- 646 5. To determine if metformin in addition to usual care reduces infant birth weight when compared to
- 647 usual care alone
- 648 6. To determine if metformin reduces the proportion of maternal morbidities when compared to usual
- 649 care alone
- 650 7. To determine if metformin in addition to usual care reduces excessive maternal gestational weight
- 651 gain (GWG)
- 652 8. To determine if participants consider metformin a more acceptable treatment than insulin
- 653 9. To determine the cost, cost effectiveness, and budget impact of metformin in addition to usual
- 654 care for GDM

655

656 **7.3. Primary and secondary outcome measures**

657

658 **7.3.1. Primary Outcome Measure**

659

660 A composite primary outcome of insulin initiation or fasting venous glucose ≥ 5.1 mmol/l on study
661 specific fasting laboratory glucose at gestational weeks 32 or 38 will be used. This approach allows us
662 to measure 'treatment failure' in two discreet ways. Introduction of insulin reflects clinically meaningful
663 hyperglycaemia, and is measured at any time during the clinical trial. In addition, a standardised
664 fasting glucose will be completed at gestational weeks 32 or 38 to capture additional participants who
665 have fasting hyperglycaemia but have not had insulin introduced during the clinical trial.

666 **7.3.2. Secondary Outcome Measures**

667

668 1. Time to insulin initiation and insulin dose required

669 2. Maternal morbidity at delivery (hypertensive disorders, antepartum and postpartum haemorrhage)

670 3. Mode and time of delivery

671 4. Postpartum glucose status, insulin resistance, and metabolic syndrome

672 5. Postpartum BMI, gestational weight gain, and waist circumference

673 6. Infant birth weight

674 7. Neonatal height and head circumference at delivery

675 8. Neonatal morbidities (Need for neonatal care unit, respiratory distress, jaundice, congenital

676 anomalies, Apgar score)

677 9. Neonatal hypoglycaemia (defined as plasma glucose <2.6mmol/L on one or more occasions

678 starting 30-60 minutes after birth)

679 10. Cost effectiveness and budget impact of metformin treatment in addition to usual care

680 11. Treatment acceptability (DTSQ and Rowan questionnaires)

681 12. Quality of Life determined by EQ5D-5L questionnaire

682

683 **8. TRIAL DESIGN**

684

685 **8.1. Design Summary**

686

687 A phase III, parallel, randomised double-blind, placebo-controlled, trial of metformin (in addition to

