- 980 • Any longstanding medical condition for which the participant is currently taking treatment

981

982 A review of all concomitant medications will be documented by interview or review of medical records
983 at the screening visit. Changes in medical history and concomitant medications will be reviewed at
984 each subsequent visit.

985

986

987

988

989 **8.4.3. Physical Assessments**

990
991 Standardised measurement of BP will be used. Weight will be measured in kg, height in meters and
992 body mass index (BMI) as kg/m². BMI will be calculated categorised according to World Health
993 Organization (WHO) standards: underweight, <18.5 kg/m²; normal, 18.5–24.5 kg/m²; overweight
994 (OW), 25–29.9 kg/m²; obese (OB), >30 kg/m². Waist circumference will be taken using a tape
995 measure half way between the hip bone and the lowest rib, about 5 cm (2 in) above the belly button.
996

997 **8.4.4. OGTT**

998
999 A 75g OGTT will be carried out at screening and 12 weeks (+/- 4 weeks) post-partum.
1000 The OGTT at screening will determine the presence of GDM according to IADPSG/WHO 2013 criteria
1001 based on any one of the following values: Fasting >/= 5.1 and <7, 1 h >/=10, and 2h >/= 8.5 and
1002 <11.1 mmol/l. Results of the post -partum OGTT will categorize participants as one of the following: 1)
1003 Negative: fasting blood glucose (FBG) < 5.6 mmol/l, 2h blood glucose <7.8 mmol/l; 2) Impaired fasting
1004 glucose (IFG) FBG >5.6 <7mmol/l; 2h blood glucose <7.8mmol/l. 3) Impaired glucose tolerance FBG
1005 5.6-7mmol/l; 2h blood glucose 7.8-11.1mmol/l. 4) Diabetic FBG >7mmol/l or 2h blood glucose
1006 >11.1mmol/l. We will use a fasting venous sample as venous glucose is more accurate than capillary
1007 measurements.
1008

1009 **8.4.5. Laboratory Tests**

1010
1011 Lab tests should be completed at the randomisation visit, 32 gestational weeks (+/- 1 week) AND at
1012 38 gestational weeks (+/- 1 week), and 12 weeks post-partum (+/- 4 weeks). If the participant is
1013 administered steroids at 32 weeks gestation or 38 weeks gestation, defer lab tests for 48 hours.
1014

1015 The following laboratory assessments will be analysed locally:
1016

1017 Randomisation: HbA1c, fasting glucose, Insulin, c-peptide, total cholesterol, high density lipoprotein
1018 (HDL) cholesterol, low density lipoprotein (LDL) cholesterol, triglycerides (Tg), urea, creatinine,
1019 alanine aminotransferase (ALT), and aspartate transaminase (AST).
1020

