1180 time, an ultrasound scan to assess fetal growth is available, which contributes to the decision making
1181 progress. If/when insulin is required; the participant is seen by the Investigator, DNS, or trained
1182 delegate for instruction on insulin type and frequency, dealing with low and high glucose and use of a
1183 glucagon pen, and sick day rules. Diet, exercise, and principles of monitoring are re-enforced at each
1184 visit and participants are encouraged to phone the service as necessary.

1185

1186 At each subsequent clinic visit, the following measurements are taken; weight, blood pressure,
1187 urinalysis, and glycated haemoglobin (HbA1C). Ultrasound scanning occurs every 4 weeks for fetal
1188 growth. Mode of delivery is individualised according to mother and fetal health, fetal growth and
1189 previous delivery type. A detailed plan is written in the case notes and protocols are available for
1190 management of delivery of women with GDM; both treated with MNT only or requiring insulin.
1191 Following delivery, all insulin is discontinued and participants resume usual diet and lifestyle.
1192 Breastfeeding is encouraged and infant glucose is tested by heel prick within the first 4 hours and as
1193 required thereafter. Prior to discharge participants are scheduled for a repeat 75g oral glucose
1194 tolerance test (OGTT) at 12 weeks post-partum through the diabetes service.

1195

1196 **9.1.2. Treatment Group**

1197

1198 Participants randomised to the treatment arm will receive active metformin in addition to usual care.
1199 Metformin tablets will be titrated according to a dosing schedule to achieve the pre-specified glucose
1200 targets (fasting \leq 5mmol/l, 1hour post prandial \leq 7mmol/l). Tablets will be in 500mg doses and will
1201 commence at 1 tablet per day (500mg) increasing to a maximum of 5 tablets per day (2500mg) as
1202 follows:

1203

- Stage 1) Day 1, 2: 1 tablet with breakfast each day
- Stage 2) Day 3, 4: 1 tablet with breakfast and 1 tablet with dinner each day
- Stage 3) Day 5, 6: 2 tablets with breakfast and 1 tablet with dinner each day

1204

1205

1206 • Stage 4) Day 7, 8: 2 tablets with breakfast and 2 tablets with dinner each day
1207 • Stage 5) Day 9, 10: 3 tablets with breakfast and 2 tablets with dinner each day
1208
1209 If a participant experiences uncomfortable side effects (e.g. diarrhoea or nausea) at any stage, the

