1319 Influenza B (Hib), Polio, Hep B, Pneumococcal (PCV), Meningococcal (Men B)
1320 g) Maternal vaccinations
1321 h) Vitamin K administration (baby only)
1322 i) Anti D for mother
1323 j) Over-the-counter antenatal multivitamins

1324 1325 9.7.1. Permitted Medications/Non-Investigational Medicinal Products

1326 The following medications are permitted for routine use throughout the duration of the trial:
1327
1328 1. Paracetamol
1329 2. Aspirin
1330 3. Low molecular weight heparin
1331 4. Antihypertensives
1332 5. Routine pregnancy supplements
1333 6. Folic Acid
1334 7. Vitamin D
1335 8. Antacids
1336 9. Prescribed medications for established chronic diseases
1337 10. Insulin

1338 Insulin taken for less than 72 hours will be recorded but will not be considered a primary outcome
1339 measure.

1340 9.7.2. Prohibited Medications

1341 The following medications are not permitted for routine use throughout the duration of the trial:

1342
1343
1344
1345
1346
1347 • Non-study oral hypoglycaemic medications
1348 • Intravascular contrast studies with iodinated materials

1349
1350 Intravascular contrast studies with iodinated materials can lead to acute alteration of renal function
1351 and have been associated with lactic acidosis in patients receiving metformin. Metformin/placebo
1352 must be discontinued prior to or at the time of the imaging procedure and not restarted until at least
1353 48 hours after, provided that renal function has been re-evaluated and found to be stable.

1354
1355 If for any clinical reason the patient requires treatment with any of the above, the patient must
1356 discontinue study treatment either temporarily or permanently and this must be documented in the
1357 CRF.
1358

1359 **9.7.3. Cautionary Medications**

1360
1361 Some medicinal products, such as NSAIDs (including selective cyclo-oxygenase (COX) II inhibitors),
1362 ACE inhibitors, angiotensin II receptor antagonists and diuretics (particularly) loop diuretics) may
1363 adversely affect renal function and may increase the risk of lactic acidosis. When starting or using
1364 such products in combination with metformin/placebo, monitoring of renal function may be required.
1365
1366 Medicinal products with intrinsic hyperglycaemic activity (e.g. systemic or local glucocorticoids and
1367 sympathomimetics) may require more frequent blood glucose monitoring.
1368
1369 As metformin is a substrate of the OCT1 and OCT2 organic cation transporters, co-administration with

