5.2 Study endpoints

5.2.1 Primary endpoint

A composite primary outcome of insulin initiation or fasting hyperglycemia (glucose ≥ 5.1 mmol/l) on study specific fasting laboratory glucose at gestational weeks 32 or 38 will be used. This approach allows us to measure 'treatment failure' in two discreet ways. The introduction of insulin reflects clinically meaningful hyperglycaemia, and is measured at any time during clinical trial. In addition, a standardised fasting glucose will be completed at gestational weeks 32 and 38, to capture additional participants who have fasting hyperglycaemia but have not had insulin introduced during the clinical trial.

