13.1 Primary Efficacy Analysis

The primary efficacy outcome is a composite of:

- Insulin initiation (Yes/No) or
- Fasting hyperglycemia ≥ 5.1 mmol/l at week 32 or 38.

Suitable numerical and graphical techniques will be used to compare the primary and secondary responses and the balance in explanatory variables at baseline. The primary analysis will be a two-sample comparison of reduction in the proportion of women needing insulin between treatment and control arms. A logistic regression model will be used to adjust for the stratifying variables, BMI and past history of GDM, along with other patient characteristics as appropriate.

A small number of participants (24) were randomised in more than one occasion for this study, each corresponding to a new pregnancy (49 in total). Note that the primary analysis described above will treat these duplicated pregnancies as independent. Although it is not expected that this issue will be influential in the overall conclusions derived from the analysis of the primary outcome, a sensitivity analysis will be performed considering only the first pregnancy per woman, among the 24 women who entered the study more than once.

A secondary exploratory analysis will involve a comparison of the time to insulin initiation between the treatment groups, initially using the log-rank test and then the proportional hazards model in order to adjust for patient characteristics as appropriate. Longitudinal data analyses based on linear mixed models will be used to evaluate the effect of intervention on secondary outcome of mean change in weight (from baseline to postpartum follow-up).

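### The protocol excludes insulin taken for less than 72 hours from the primary outcome, but every section that defines the primary outcome counts any insulin initiation

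*Protocol*

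**What the plan says.** The duration rule appears once, in protocol 9.7.1, after the list of permitted medications: "Insulin taken for less than 72 hours will be recorded but will not be considered a primary outcome" measure.

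The sections that define the primary outcome do not carry it:

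- Protocol 7.3.1 describes the introduction of insulin as clinically meaningful hyperglycaemia "and is measured at any time during the clinical trial".
- Protocol 11.5.1 lists insulin initiation as a yes/no item.
- SAP 5.2.1 repeats the protocol's description: "and is measured at any time during clinical trial".
- SAP 13.1 gives the component as "Insulin initiation (Yes/No) or" fasting hyperglycaemia at week 32 or 38.

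Two other protocol sections bear on how the rule works near term. Section 9.1.4 allows insulin to start at any clinic visit when home readings are out of target, and the intervention runs to birth. Section 9.1.1 says: "Following delivery, all insulin is discontinued and participants resume usual diet and lifestyle".

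**The concern.** The insulin component is half of the primary composite, and its definition depends on where one looks. An analyst programming from the SAP alone would score every initiation as an event. One who also applies protocol 9.7.1 would leave short courses out. SAP 10.1 provides for validation by an independent statistician, so two people could each follow a trial document faithfully and obtain different primary event counts.

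The ambiguity reaches further than the primary test:

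- Time to insulin initiation (SAP 13.1) has no stated duration rule.
- The cost-effectiveness analysis (SAP 13.3) uses the primary clinical outcome.
- The reduction to 535 participants (SAP 8.1) rests on the observed overall proportion taking insulin, and the SAP does not say whether short courses were included.

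Timing matters because SAP 8.2 has the primary outcome analysed with the randomisation codes after the last birth and before database lock. A definition chosen after that could be seen as chosen with knowledge of the result.

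**Working it through.** **Texts side by side**

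| Place | Insulin component | Minimum duration |
|---|---|---|
| Protocol 9.7.1 | Insulin under 72 hours is recorded but is not a primary outcome | 72 hours |
| Protocol 7.3.1 | Introduction of insulin at any time | None stated |
| Protocol 11.5.1 | Initiation, yes/no | None stated |
| SAP 5.2.1 | Introduction of insulin at any time | None stated |
| SAP 13.1 | Initiation, yes/no | None stated |

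The protocol is therefore inconsistent within itself as well as with the SAP.

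**Delivery**

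Insulin can start at any clinic visit (9.1.4) and stops after delivery (9.1.1). A woman who starts less than 72 hours before delivery cannot reach 72 hours. Under 9.7.1 she is a non-event unless her week 32 or 38 fasting glucose was at least 5.1 mmol/l.

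**The plan's own sample size**

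Inputs from SAP section 7 are 40% v 28%, alpha 0.05 (two-sided assumed, as sidedness is not stated), 80% power, 1:1 allocation and 5% drop-out.

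- Without continuity correction, n per arm = [1.96√(2 × 0.34 × 0.66) + 0.8416√(0.40 × 0.60 + 0.28 × 0.72)]² / 0.12² = 243.4, rounded up to 244.
- With continuity correction it is 260 per arm, or 520 in total.
- 260 / 0.95 = 273.7, rounded up to 274 per arm. The total is 548, close to the stated 550.
- The other planning pair, 35% v 23.45% (a 33% relative reduction), also gives 548.
- Diluting the metformin rate for the stated 8% non-adherence does not reproduce 550. The total becomes 612 without the correction or 650 with it.

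The finding does not depend on this figure, which only supplies a base for the illustration below.

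**How many women could be affected**

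No document gives the frequency of short courses. Assume 1% to 5% of women: 535 × 0.01 = 5.35 and 535 × 0.05 = 26.75, so about 5 to 27 women. This is an upper limit for the composite, because any of them with a qualifying fasting glucose is an event under either text.

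**Effect on power**

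With n = 550 × 0.95 / 2 = 261.25 per arm:

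Power = Φ{[|p1 − p2|√n − 1.96√(2p̄(1 − p̄))] / √(p1(1 − p1) + p2(1 − p2))}, where p̄ is the mean of p1 and p2.

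At 40% v 28%: (1.9396 − 1.3130) / 0.6645 = 0.943, so the base power is 82.7%.

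| Assumed x | Short courses counted, adding x points to each arm | Rule removes a share x of events in each arm |
|---|---|---|
| 1% | 82.2% | 82.1% |
| 3% | 81.3% | 81.0% |
| 5% | 80.5% | 79.7% |

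Against 82.7%, the movement is 0.5 to 2.2 points in the first scenario and 0.6 to 3.0 in the second. In the second, x is a share of events, so it involves fewer women than the 5 to 27 above. At 535 participants less 5%, the base power is 81.7%.

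**Effect on the estimate**

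Suppose a share s of otherwise event-free women in both arms is counted, so p′ = p + (1 − p)s.

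- At s = 1%: 0.2872 / 0.406 = 0.707.
- At s = 5%: 0.316 / 0.430 = 0.735.

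The relative risk moves from 0.70 to between 0.71 and 0.74, and the difference from 12.0 to between 11.9 and 11.4 points. These use insulin-only planning rates. Fewer women are event-free on the composite, so the shifts are probably overstated.

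**The case against.** The strongest reply is that the SAP is silent and does not contradict the rule. It never says short courses count. The phrase about any time can be read as governing when insulin starts, not how long it lasts. The SAP preface lists protocol version 6 among its sources and sends readers to the protocol for details. On that reading the specific rule in 9.7.1 simply qualifies the general term. This is a possible reading, but nothing in the SAP says so, and the protocol's own outcome sections omit the rule too. An analyst should not have to infer a primary event definition from a list of permitted medications.

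It is also fair that the effect is likely to be small and that the 1% to 5% rate is assumed. Both points stand.

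Three stronger inferences are tempting but not supported:

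- **Short courses given for steroids or labour are being scored as treatment failure.** No section links short insulin courses to either, and the protocol gives no reason for the 72-hour rule. The steroid wording in protocol 8.4.5, "administered steroids at 32 weeks gestation or 38 weeks gestation, defer lab tests for 48 hours", concerns the timing of blood tests, not insulin. The trigger in 9.1.4 already excludes out-of-target readings that have an explanation.
- **The rule discards many true late failures, unequally by arm.** The gap near delivery follows from the text, but its size is unknown and the week 38 glucose will catch some of these women. That metformin would change delivery timing enough to matter is speculation.
- **The SAP has deliberately dropped the rule.** The SAP does not mention the rule, so silence is all that can be shown.

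**Conclusion.** The concern holds as a conflict over the primary event. Protocol 9.7.1 excludes insulin taken for less than 72 hours, while the four endpoint sections set no minimum duration and do not refer to it. Confidence in the textual conflict is high.

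Its size is not known. The illustrative range is about 5 to 27 of 535 women on the insulin component and roughly 0.5 to 3 points of power. It rests on the assumed 1% to 5%, on insulin-only planning rates, on equal proportions in the two arms, and on a two-sided test. A reader might infer that the treatment effect is biased, but the documents do not show that. What they show is an outcome that can be scored in two ways, with no statement of which applies. It should be settled before unblinding, because a later choice could depend on the data.

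**What to change.** Before the randomisation codes are used for the analysis in SAP 8.2:

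1. Reconcile protocol 7.3.1, 9.7.1 and 11.5.1 with SAP 5.2.1 and 13.1. State one insulin-event definition, carrying the 72-hour rule of 9.7.1, in SAP 5.2.1, SAP 13.1 and protocol 7.3.1.
2. Apply the same definition to time to insulin initiation.
3. State how insulin cut short by delivery is classed. Use the insulin start date and the delivery date, if the CRF holds both, so that no judgement about why insulin stopped is needed.
4. Add one sensitivity analysis of the primary outcome that counts any insulin initiation.

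The sponsor should confirm what the CRF holds. In protocol Figure 2, insulin initiation data are scheduled from randomisation through the prenatal visits but not at the delivery visit. Concomitant medications are reviewed at delivery, and delivery date and time are collected. The documents do not show that a reason for stopping insulin is captured, so the definition should not depend on one.

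The cost is a wording change in both documents, one extra table and a small change in the event count. No clinical procedure changes.

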10.2.1. Assessment of seriousness

1561

The investigator should make an assessment of seriousness as defined in section 10.1.3.

1562

1563

1564

10.2.2. Assessment of causality

1565

1566

All adverse events judged by either the investigator or the sponsor as having a reasonable suspected causal relationship to an investigational medicinal product or with the non-investigational medicinal product qualify as adverse reactions.

1567

1568

1569

1570

1571

The investigator must make an assessment of whether the AE/SAE is likely to be related to treatment

1572

according to the following definitions:

1573

- Unrelated: Where an event is not considered to be related to the study medication.
- Unlikely: where a temporal relationship to the study medication makes a relationship improbable (but not impossible) and disease or other drugs provide plausible explanations.
- Possible: Although a relationship to the study medication cannot be completely ruled out, the nature of the event, the underlying disease, concomitant medication or temporal relationship make other explanations possible.
- Probable: The temporal relationship and absence of a more likely explanation suggest the event could be related to the study medication.
- Definite: Plausible temporal relationship and cannot be explained by disease or other drugs.

1574

The causality assessment given by the investigator should not be downgraded by the sponsor. All AEs/SAEs judged as having a reasonable suspected causal relationship (e.g. definite, possible, probable) to the study medication will be considered as ARs/SARs. All AEs/SAEs judged as being related (e.g. definite, possible, probable) to the non-IMP will also be considered to be ARs/SAR. All AEs/SAEs judged as being related (e.g. definite, possible, probable) to an interaction between the IMP and non-IMP will also be considered to be ARs/SAR.

1575

1576

1577

1578

1579

1580

1581

1582

1583

1584

1585

1586

1587

1588

1589

1590

1591

Alternative causes such as natural history of the underlying disease, concomitant therapy, other risk

1592

factors and the temporal relationship of the event to the treatment should be considered.

1593

The causality assessment will also be reviewed by the sponsor.

1594

1595

10.2.3. Assessment of severity

1596

1597

The investigator will make an assessment of severity for each AE/SAE and record this on the CRF according to one of the following categories:

1598

1599

- Mild: An event that is easily tolerated by the participant, causing minimal discomfort and not interfering with every day activities.
- Moderate: An event that is sufficiently discomforting to interfere with normal everyday activities.
- Severe or medically significant: An event that prevents normal everyday activities.
- Life threatening: An event that has life-threatening consequences

1600

1601

1602

1603

1604

1605

1606

1607

Note: the term 'severe', should not be confused with 'serious' which is a regulatory definition based on

1608

participant/event outcome or action criteria

1609 **10.2.4. Assessment of expectedness**

1610

1611 An expectedness assessment will be carried out by the sponsor for each serious adverse reaction to
1612 the IMP or an interaction between the IMP and non-IMP. The expectedness of a serious adverse
1613 reaction will be determined by the sponsor according to the reference safety information as contained
1614 in section 4.8. of the SmPC for Metformin.

1615

1616 **10.3. Reporting Responsibilities of the investigator**

1617

1618 **10.3.1. Adverse Events/Serious Adverse Events**

1619

1620 Any AE whose onset occurred after the time of informed consent and the last completed visit,
1621 observed by the investigator or reported by the participant, whether or not attributed to the study
1622 medication, will be recorded on the AE form in the CRF. The Site Investigator or delegate will follow
1623 AE's and SAE's reported during the treatment period until resolved, considered stable, or completion
1624 of participant participation in the EMERGE trial (i.e. 12 week Postpartum Visit). Follow up information
1625 will be sought and submitted as it becomes available. All SAEs will be followed up until resolution or
1626 they are clearly determined to be due to a participant's stable or chronic condition or intercurrent
1627 illness(es).

1628

1629 The following information will be recorded in the adverse event form: Adverse event term, description,
1630 date of onset, outcome, date of resolution, seriousness, severity, assessment of relatedness to the
1631 study medication, assessment of relatedness to non-IMP, and assessment of relatedness to
1632 interaction between IMP and non-IMP, and action taken with study drug. The Site Investigator is
1633 responsible for the assessment of severity (intensity), causality/relatedness to IMP, non-IMP or an
1634 interaction between IMP and non-IMP, for all AEs and SAEs. An SAE should also be substantiated by
1635 a source document(s). Follow-up information should be provided as necessary.

1636

1637 It will be left to the investigator's clinical judgment whether or not an AE is of sufficient severity to
1638 require the participant's removal from medication. A participant may also voluntarily withdraw from
1639 medication due to what he or she perceives as an intolerable AE. If either of these occurs, the
1640 participant must undergo an end-of-study assessment and be given appropriate care under medical
1641 supervision until symptoms cease or the condition becomes stable.

1642

1643 **10.3.2. Timelines for reporting**

1644

1645 Adverse event information will be reported by site personnel in a timely fashion from the time the site
1646 becomes aware of the event.

1647

1648 Serious adverse event information will be reported by site personnel within 24 hours to the sponsor
1649 from the time the site becomes aware of the event, except for those that the protocol identifies as not
1650 requiring immediate reporting. The site team are considered aware of an adverse event from the time
1651 of first notification of the first member of the EMERGE site team, as per the Site Delegation Log. All
1652 SAE's will be submitted by the site by completing the required fields on the AE CRF within 24 hours of
1653 site awareness of the event. A valid SAE report must include all of the following:

1654

- 1655 • Adverse event term (based on what is known at the time of reporting)
- 1656 • Seriousness criteria
- 1657 • Severity

1658 • Causality assessments (for metformin/placebo, insulin [if applicable] and the potential
1659 interaction between metformin/placebo and insulin [if applicable])
1660 • Investigator sign-off

1661
1662 The immediate report will be followed by detailed, written reports. The immediate and follow-up
1663 reports will identify participants by unique code numbers.
1664

1665 **10.3.3. Safety Reporting for Non-IMP**

1666
1667 Insulin is considered a non-IMP and therefore must follow safety reporting guidelines for non-IMP.
1668 All AEs and SAEs considered by the investigator to be related to the non-IMP will be reported to the
1669 sponsor within the required timeframes (section 10.3.2).
1670 All AEs and SAEs which are considered by the investigator to be related to an interaction between
1671 IMP and non-IMP will be reported to the sponsor within the required timeframes (section 10.3.2).
1672

1673 **10.4. Reporting responsibilities of the sponsor**

1674
1675 **10.4.1. Regulatory Authorities**
1676
1677 The sponsor will keep detailed records of all adverse events which are reported to him by the
1678 investigator or investigators. The sponsor will report all SUSARs to the competent authority (HPRA) or
1679 EudraVigilance (as required) and the approving ethics committees concerned, and all principal
1680 investigators. Fatal or life-threatening SUSARs must be reported within 7 days.
1681

1682 If the initial report is incomplete, e.g. all the information/assessment has not been provided, the
1683 sponsor will submit a completed follow up report within an additional eight days.
1684

1685 SUSARs which are not fatal and not life-threatening are to be reported within 15 days to the sponsor.
1686 If significant new information on an already reported case is received by the sponsor, the clock starts
1687 again at day zero, i.e. the date of receipt of new information. This information will be reported as a
1688 follow-up report within 15 days.
1689

1690 **10.4.2. Safety Reports**

1691
1692 The sponsor will distribute masked expedited SUSAR reports, to each participating Site Investigator,
1693 as appropriate.
1694 SUSARs of which the treatment allocation of the participant is un-blinded should be reported by the
1695 sponsor to the national competent authority as well as the Ethics Committee.
1696

1697 **10.4.3. Annual Reports**

1698
1699 In addition to the expedited reporting above, the sponsor shall submit once a year throughout the
1700 clinical trial or on request, a safety report to the competent authority (HPRA) and ethics committees.
1701 The annual safety report will be presented in the development safety update reports (DSUR) format
1702 as per ICH guideline E2F - Note for guidance on DSUR.

1703

1704 **10.4.4. Safety reports for non-IMP**

1705 The sponsor will report SARs for non-IMP to the Regulatory Authorities or the marketing authorisation
1706 holder. The sponsor will report SUSARs for interactions between the IMP and non-IMP to the
1707 competent authority (HPRA) or EudraVigilance (as required) and Ethics Committee.

1708

1709 The sponsor will distribute masked expedited SUSAR reports for interactions between IMP and non-
1710 IMP to each participating Site Investigator, as appropriate.

1711

1712 **10.5. Data safety monitoring board (DSMB)**

1713

1714 A DSMB is established and members will serve in an individual capacity and provide their expertise
1715 and recommendations. The primary responsibilities of the DSMB will be to:

1716

- 1717 1. Become familiar with the research protocol and the procedures for data safety/monitoring.
- 1718 2. Review interim analyses of outcome data/adverse event reports.
- 1719 3. Make written recommendations to the TSC concerning the continuation, modification, or
1720 termination of the trial.
- 1721 4. Consider any requests for release of interim trial data and make recommendations to the TSC
1722 on the advisability of this.
- 1723 5. Review major proposed modifications to the study prior to their implementation (e.g.,
1724 termination, increasing target sample size).
- 1725 6. Maintain confidentiality during all phases of DSMB review and deliberations.
- 1726 7. Review SAEs and SUSARs as appropriate

1727

1728 The responsibilities of the DSMB are outlined further in the DSMB charter. The membership of the
1729 DSMB reflects the professions necessary to interpret the data and results from the study and to
1730 evaluate participant safety fully.

1731

1732 **10.6. Trial Steering and Advisory Group**

1733

1734 The purpose of the TSAG is to provide strategic oversight for the overall direction and strategy for a
1735 clinical trial. The primary responsibilities of the TSAG are:

1736

- 1737 1. To contribute to the design of the study
- 1738 2. Increase information exchange at an early stage of trial development
- 1739 3. Increase the efficiency of clinical trial collaboration
- 1740 4. To monitor and review a) Recruitment progress, b) Quality control, c) Ethical amendments, d)
1741 Financial aspects, and e) Publications
- 1742 5. To determine action points to facilitate the satisfactory progress of the EMERGE study.

1743

1744 This committee includes investigators, other experts not otherwise involved in the trial, and
1745 representative of the sponsor. The responsibilities of the TSAG are outlined further in the TSAG
1746 charter.

1747

1748 **11. STATISTICS**

1749

1750 **11.1. General Considerations**

1751 General description of the statistical methods is outlined below. A more detailed statistical analysis
plan (SAP) will be provided in a separate document. The SAP document will provide a more technical

1752 and detailed elaboration of the principal features of the planned analyses. The SAP will be finalised
1753 prior to study enrolment, at the latest before any substantial information in the trial has accumulated.
1754

1755 Analyses will be performed using R software.
1756

1757 11.2. Determination of sample size

1758 Our sample size is based on the following; a) 35% of participants will require insulin in the control
1759 arm, based on information from the MiG trial and data from University Hospital Galway and University
1760 Hospital Cork; b) ability to detect a minimum of 33% relative risk reduction in proportion of participants
1761 requiring insulin in the experimental (metformin) group (40% to 28% absolute reduction; in the MiG
1762 trial only 40% of participants on metformin required insulin); c) significance level of 0.05 and 80%
1763 power; d) drop-out rate of 5% or less; and e) non-adherence rate of 8% in metformin group. Based on
1764 these assumptions, we require a total of 550 participants. This sample size will also have 80% power
1765 to demonstrate a difference between the proportions of 12% or more (i.e. a reduction from 60-48%) in
1766 the secondary outcome of excessive GWG.
1767

1768 There are 7,000 deliveries annually in participating sites. From ATLANTIC DIP 1 we have identified a
1769 prevalence of 12.4% for GDM using IADPSG criteria. In our previous universal screening project, we
1770 had a consent rate of 75% but a testing rate of circa 50%. On a second study examining uptake rates
1771 in primary v secondary care, the screening uptake rate was 88% for screening in secondary care.
1772 With prevalence of 12% we would expect to diagnose upto 840 pregnancies with GDM annually. For
1773 the secondary outcome of baseline to post-partum weight change, there is a greater concern with loss
1774 to follow-up, as post-pregnancy follow-up rates have been reported in some studies to be less than
1775 70%. For this outcome, even with a loss-to follow-up of 50% the resulting 138 per arm will have 80%
1776 power, at the 0.05 significance level, to detect a minimum difference in mean weight change of
1777 1.36kgs (assuming a standard deviation of the change in weight of 4kgs). However, every effort will
1778 be made to achieve follow-up rates of >95% for post-partum follow-up, and we will implement a
1779 number of strategies to enhance follow-up for this outcome (e.g. home monitoring of weight).
1780

1781 11.3. Analysis Sets

1782 11.3.1. Intention-to-Treat Analysis Set

1783 The intention-to-treat analysis set, also termed full analysis set in the International Conference on
1784 Harmonization (ICH) E9 guideline, will include all randomized participants.
1785

1786 11.3.2. Safety Analysis Set

1787 The safety analysis set will include all randomized participants who received at least one dose of
1788 study medication.
1789

1790 11.4. Demographic and baseline disease characteristics

1791 Demographic and baseline characteristics of the study population will be summarized using graphical
1792 displays and descriptive statistics for each treatment group.
1793

1794

1800 **11.5. Effectiveness Analysis**

1801

1802 Suitable numerical and graphical techniques will be used to compare the primary and secondary

1803 responses and the balance in explanatory variables at baseline. The primary analysis will be a two-

1804 sample comparison of reduction in the proportion of participants needing insulin between treatment

1805 and control arms using an exact test for a binomial response.

1806

1807 We will also conduct a logistic regression analysis, to adjust for differences of baseline co-variates

1808 between treatment groups. Several strategies for including explanatory variables will be employed

1809 where penalisation for multicollinearity will be achieved using ridge penalties. Following this the most

1810 parsimonious subset of predictor variables will be identified using computationally intensive data

1811 driven techniques such as the classification trees and the Lasso penalty.

1812

1813 A secondary exploratory analysis will involve a comparison of the time to insulin initiation between the

1814 treatment groups, initially using the log-rank test and then the proportional hazards model in order to

1815 adjust for patient characteristics as appropriate. Repeated measures ANOVA will be used to evaluate

1816 the effect of intervention on secondary outcome of mean change in weight (from baseline to post-

1817 partum follow-up).

1818

1819 **11.5.1. Primary Effectivness Outcomes**

1820

1821 The primary efficacy outcome is a composite of:

1822

- Insulin initiation (Yes/No)
- Fasting glucose value <5.1 mmol/l and ≥ 5.1 mmol/l

1823

1824 **11.5.2. Secondary Effectiveness Outcomes**

1825

1826 Secondary efficacy outcomes include:

1827

